Secondary

To determine the effectiveness of 6 months closed-loop compared with manually determined insulin dosing on glucose control, psychosocial well-being, sleep, cognitive functioning, ECG and health economics measures in adults with type 1 diabetes.

Section 3: Study Methods

Trial design

HCL-Adult is a multicentre, open label, parallel-group, superiority randomized clinical trial with equally sized treatment groups.

The intervention will last for 26 weeks, with an additional minimum 5 week period of active run-in which includes education (pre-randomisation). The exact duration of run-in will depend on individual training requirements. The study flow is presented in Figure 1.

Randomization

Group allocation (HCL or continuing standard care) will be random with a 1:1 ratio using minimization with 3 stratification variables, all of which are expected to be highly prognostic of primary outcome. These minimization variables are: 1) % time in target range pre-randomisation (dichotomised into <= 55% and > 55%); 2) study centre (7 sites); and 3) insulin delivery modality at enrolment (MDI or IPT). Due to the nature of the intervention, blinding of participants and investigators is not possible.

Sample size

Sample size calculation is based on a parallel design with 2 equally sized groups.

Assumptions used were derived from JDRF CGM randomized clinical trials [8, 9] that recruited a sample of 69 adults (25-70 years old) with type 1 diabetes and a baseline HbA1C < 10.5%, 86% of whom were using IPT and 14% using MDI. All participants had masked CGM data at randomization and at 6 months. Study investigator [name], personal communication, provided estimates of the effective standard deviation of percentage time spent in target glycaemic range at 6 months (adjusted for baseline) which was 9% (95% CI 8% to 12%) for pump users and 10% (95% CI 7% to 19%) for MDI users.

To detect a difference in percentage time in target glycaemic range of 5% with 80% power and 5% type I error rate assuming a common standard deviation of 9%, a total of 104 participants are needed. Allowing a drop-out rate of 10% a total of 120 people will be recruited, 60 randomized to HCL while 60 randomized to control group.

A more conservative scenario with a dropout rate of 20%, and unequal SDs of 12% and 19% for IPT and MDI users, respectively, increases the minimum detectable absolute difference to 9% with a power of 80%.

Framework

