This study is a superiority study with all analysis being performed on this basis.

Statistical interim analyses and stopping guidance

No interim analysis is planned. The study device has been previously proven to be safe for people with type 1 diabetes [10]; therefore, early stopping due to safety issues is not expected. However, safety recommendations will be made by an independent Data Safety Monitoring Committee (DSMC).

Timing of final analysis

The primary outcome and secondary glucose outcomes will be analysed collectively at the conclusion of the study. Other secondary outcomes will be analysed separately at the end of the study.

Health economic outcome and biomarkers will be analysed at a later date after additional funding is obtained.

Timing of outcome assessments

Pre-randomisation outcomes are collected at Visits 3-6, mid-study outcomes are collected at Visits 9-11 and end-of-study outcomes are collected at Visits 12-15 (Figure 1)

[figure not shown]

Figure 1: Study flow and timing of outcome assessments

Section 4: Statistical principles

Confidence intervals and p values

All hypothesis testing will be two-sided with an α of 0.05, with reported 95% confidence intervals.

No corrections for multiplicity are planned to control Type I error; rather, the effectiveness of the intervention will be assessed based on the clearly specified primary outcome; secondary outcomes are exploratory in nature and will be labelled as such in publications arising from the study. A transparent approach to reporting results will be taken, with the list of all pre-specified secondary outcomes included in every publication resulting from this study (this list would include a reference to relevant publication if results already published).

Results will be interpreted in light of the number of comparisons and where multiple comparisons indicate multiple effects, the consistency of these results will be discussed.

Adherence and protocol deviation

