Section 6 Analysis

Primary outcome

Outcome definition

Primary outcome is the percentage of time spent in target glucose range (3.9-10 mmol/L) measured by masked CGM over 3 weeks starting at 23 weeks post randomization (\pm 3 weeks) (glucose measured at 5-min intervals). Participants with a low number of available CGM readings in one or more weeks will have the CGM repeated and may have up to 5 weeks of masked CGM collection. To accurately represent participant's glycaemic status, only days with at least 70% valid CGM readings will be used (>= 202 valid readings) [11]. The percentage of time spent in target glucose range will be calculated by dividing the number of sensor readings falling in the range 3.9 – 10 mmol/L by the total number of sensor readings and multiplying by 100 over the whole period of masked CGM collection. If the participant has less than 10 representative days [11] their outcome will be counted as missing (individual glucose values will not be imputed).

Analysis methods

To test for an effect of the treatment group on the primary outcome, an ANCOVA including treatment arm and baseline percent time in target range will be conducted. The primary outcome will be analysed on an intention-to-treat basis on the entire study population with missing outcome data imputed using multiple imputations under missing at random (MAR) assumption (overall time in range will be imputed rather than single glucose values, see section on Missing data).

Results will be presented as the mean difference in the percent time in target range between treatment arms at the end of the study with 95% confidence interval and p value.

Model residuals will be visually inspected to test the assumptions of the model. In the event of violations to homoscedasticity and non-normal distribution, the outcome will be transformed using a natural logarithm. If the ANCOVA model still displays poor fit, non-parametric analysis (Wilcoxon rank sum test) will be employed.

Sensitivity analyses

- 1. ANCOVA with adjustment for factors used in the minimisation will be conducted (study centre 7 categories, insulin delivery modality 2 categories).
- 2. Replication of primary outcome analysis in complete case population (missing completely at random (MCAR) assumption)
- 3. Replication of primary outcome analysis in full study sample using multiple imputation of missing data under missing not at random (MNAR) assumption (see section Missing data)

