- 4. Replication of primary outcome analysis in per-protocol population (see population definitions).

Planned subgroup/interaction analyses

The differential effect of the intervention on the primary outcome based on insulin regimen at enrolment (IPT or MDI) will be examined using a linear regression including terms for treatment group, regimen, a treatment group by regimen interaction, and baseline time in range.

Missing data

See Missing data section below.

Secondary outcomes

1. Glucose control

Outcome definition

Percent time in ranges (day/night/overall)

Percent time spent in the following ranges will be examined.

- 3.9 10.0 mmol/L
- < 2.8 mmol/L

- < 3.0 mmol/L*

- < 3.3 mmol/L

- < 3.9 mmol/L

- 3.9 7.8 mmol/L
- > 10.0 mmol/L
- > 13.9 mmol/L
- > 16.7 mmol/L

Percentage of time spent in each glucose range will be calculated by dividing the number of sensor readings falling in the range by the total number of valid sensor readings and multiplying by 100. This will be performed separately for day (6:00-23:59), night (00:00-5:59) and overall. Values will be calculated at baseline, mid-study, and end-of-study using masked CGM collection.

- Mean glucose level, standard deviation and coefficient of variation (SD/mean)

These metrics will be calculated using valid readings only, separately for day (6:00 - 23:59), night (00:00 - 5:59) and overall. Values will be calculated at baseline, mid-study, and end-of-study using masked CGM collection.

Fasting capillary blood glucose

Fasting capillary blood glucose is defined as the first capillary blood glucose taken between 5 am and 9 am during the period of masked CGM collection. These are recorded separately in blood glucose meters.

- HbA1c

HbA1c is measured from blood sample at enrolment, randomisation, mid-study (3 months post randomisation) and end-of-study (6 months post randomisation).

- 1.5-anhydrogluticol

This biomarker is measured at randomisation and end-of-study.

^{*}This outcome was not part of initial protocol, however it was added due to the position statement of the American Diabetes Association and the European Association for the Study of Diabetes published in 2017 ([12])

- Hypoglycaemic events

Events of symptomatic hypoglycaemia are defined as episodes of hypoglycaemia with glucose level < 3.5 mmol/L confirmed by a finger prick and requiring carbohydrate rescue. These events are self-reported and collected in participant's diary throughout the study.

Analysis method

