- Severe hypoglycaemia, defined as hypoglycaemia requiring the assistance of another person to actively administer carbohydrate, glucagon, or take other corrective actions (n)
- Infections and inflammation at sensor and insulin delivery line insertion sites

Analysis method

Safety outcomes will be presented as a count of events for each treatment group and percentage of participants experiencing at least one event in each treatment group. No formal statistical tests will be performed.

Sensitivity analysis

Due to exploratory nature of the outcomes, no sensitivity analysis will be performed.

Subgroup analysis

Separate analysis for each regimen will be performed.

Missing data

Baseline variables are expected to have minimal missing data. Missing data in outcome variables are more likely to be arbitrary missing than monotone missing, therefore missing data will be multiply imputed using a multivariate normal regression imputation method given smaller sample size [14]. All the imputations will be performed separately for each treatment arm [15]. Baseline and midstudy variables will be considered to be included in the model based on their correlation with the outcome. The number of imputations will be contingent upon the missing proportion: if $\leq 30\%$ missing, 20 imputations will be generated; if >30% missing, 40 imputations will be generated [16].

In the event of violations to regression assumptions, hence non-parametric methods are required, simple imputation will be performed, replacing the missing value with the median of the treatment arm.

Secondly delta-adjusted multiple imputations will be conducted under the missing not at random (MNAR) assumption using the following deltas: -1SD, +1SD.

If unexpected patterns of missing data are found, additional post-hoc sensitivity analysis will be performed.

Additional analyses

1. Missing data patterns

The patterns of missing data overall and within masked CGM will be explored, in particular time of the day and day of the week. Further analysis might be performed based on initial results.

- 2. Study process measures
 - a. Time from enrolment to randomisation (days)
 - b. Days between randomisation and end-of-study visit
- c. Amount and percent time valid sensor readings during masked CGM periods Median, interquartile range, minimum and maximum values will be presented overall and separately for each treatment group.

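### Imputation variables are chosen by correlation with the outcome, so insulin regimen has no guaranteed place in the imputation model; if it is left out, the planned treatment-by-regimen interaction is attenuated by up to about the missing fraction.

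*SAP*

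**What the plan says.** - **Imputation (SAP, Missing data).** Missing outcomes are multiply imputed by multivariate normal regression, separately in each arm. On the content of the model the SAP says only: "Baseline and midstudy variables will be considered to be included in the model based on their correlation with the outcome". It does not give a cut-off, say whether correlation is judged within arm or across arms, or list variables that are always included.
- **Subgroup model (SAP, Primary outcome, Planned subgroup/interaction analyses).** The effect by regimen is to be examined with a "linear regression including terms for treatment group, regimen, a treatment group by regimen interaction, and baseline time in range". A pointer to the Missing data section follows directly.
- **Regimen elsewhere.** It is one of three minimisation factors, all of which the SAP expects to be strongly prognostic (Randomization). It is also an adjustment factor in sensitivity analysis 1 ("study centre 7 categories, insulin delivery modality 2 categories").
- **Expected loss.** The Sample size section allows for 10% dropout, and for 20% in its cautious scenario. The primary outcome also counts as missing when a participant has fewer than 10 representative CGM days.

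**The concern.** An imputation model should contain every variable of the analysis model that will be fitted to the imputed data. Imputing by arm lets a treatment interaction survive, but only for variables that are in each arm's model. If regimen is absent, the imputed end-of-study values carry no MDI-versus-IPT difference beyond what the other predictors convey, and the interaction is pulled toward zero.

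Marginal correlation with the outcome is a poor entry test for this purpose, because the coefficient of interest is conditional on baseline. If MDI users start lower and gain more on closed loop, regimen may show little marginal correlation with end-of-study time in range in that arm and still matter given baseline. At stake is the only subgroup analysis planned for the primary outcome.

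**Working it through.** **1. The SAP's own figures reproduce.** Inputs from the Sample size section: a 5-point difference, SD 9, 80% power, two-sided 5% error. The result is given there as "assuming a common standard deviation of 9%, a total of 104 participants are needed".
- Normal approximation: n per arm = 2 × (1.96 + 0.8416)² × (9/5)² = 50.9, so 51 per arm, 102 in total. The noncentral t version gives 52 per arm, 104 in total (power 0.801), as stated.
- 104/0.90 = 116; the plan recruits 120.
- Cautious scenario: pooled SD = √((12² + 19²)/2) = 15.9. With 48 per arm the detectable difference is 2.80 × 15.9 × √(2/48) = 9.1 (stated 9%).

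The SAP gives no figure for bias in the interaction.

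**2. Expected attenuation.** Let m be the missing fraction and θ the true interaction, that is, the regimen difference given baseline on closed loop minus that in control.
- Regimen omitted, baseline time in range only: imputed values carry no regimen difference given baseline, so estimate ≈ (1 − m)θ.
- Regimen omitted, mid-study time in range included and observed, with the same interaction at mid-study: imputed values recover a share b of the difference, where b is the slope of the end-of-study on the mid-study value given baseline. So estimate ≈ [1 − m(1 − b)]θ. With b ≈ 0.7 this is (1 − 0.3m)θ.

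**3. Simulation.** 1,500 trials per scenario.
- From the SAP: 60 per arm, half MDI, residual SD 9, imputation by arm, 20 imputations, and the SAP's interaction model.
- Assumed, not in the SAP: θ = 5 points, m = 10%, 20% or 30%, baseline slope 0.6, residual correlation of mid-study with end-of-study 0.7, mid-study complete.

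Ratio of estimated to true interaction:

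| Missing | 1 − m | Regimen omitted, baseline only | 1 − 0.3m | Regimen omitted, mid-study included | Regimen included |
|---|---|---|---|---|---|
| 10% | 0.90 | 0.91 | 0.97 | 0.97 | 0.99 |
| 20% | 0.80 | 0.78 | 0.94 | 0.94 | 0.97 |
| 30% | 0.70 | 0.69 | 0.91 | 0.93 | 0.99 |

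With an empirical SE near 3.5, the simulation error is about 3.5/√1500 = 0.09 points, or 0.018 on the ratio scale.

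A separate simulation with θ = 6 gave 0.90, 0.81 and 0.71 with regimen omitted and baseline only, and 0.96 to 0.98 with regimen included. With regimen omitted and complete mid-study time in range, the loss was about 0% to 8%.

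**4. Would the rule leave regimen out?** The SAP gives no cut-off; |r| ≥ 0.3 is assumed.
- Screened within arm, θ = 5: regimen enters the closed-loop arm's model in 26% to 29% of trials (ratios 0.94, 0.91, 0.82).
- Screened within arm, θ = 10: it enters in about 80% (ratios 0.98 and 0.97 at 10% and 20% missing).
- Screened on both arms together: it enters in 1% to 3% (θ = 5) or 10% to 12% (θ = 10), with almost full attenuation.
- Screened within arm, MDI users starting lower and gaining more (θ = 6): it enters in 13% to 19%.

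**5. What it costs.** With regimen omitted, 95% interval coverage stayed at 96% to 98%. At 20% missing, power for the interaction was 0.54 with regimen omitted against 0.75 with it included (θ = 10), and 0.13 against 0.25 (θ = 5).

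**The case against.** The best defence has four parts.
- **Wording.** The sentence can be read as choosing auxiliary variables only; the SAP nowhere says that analysis-model variables may be dropped. That is fair, but it nowhere says that they are kept.
- **Selection.** The SAP expects regimen to be prognostic, and since imputation is by arm, within-arm screening is the natural reading. That helps when the interaction is large. At 5 points, selection still fails in most simulated trials.
- **Mid-study data.** The rule admits mid-study variables, and the choice of a method for arbitrary missingness suggests that several incomplete variables are imputed jointly. This stands as a limit on size. But mid-study time in range is also only a candidate, and it does not exist for participants who leave before that assessment.
- **Size against noise.** The SE of the interaction is about 4 × 9/√108 = 3.5 points at 10% missing and 4 × 9/√96 = 3.7 at 20%. For a 6-point interaction the largest bias is 0.6 and 1.2 points, or 0.17 and 0.33 SE, in an analysis for which the trial was not sized. This stands too.

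Four stronger readings are tempting and not supported.
- *The interaction always shrinks by the missing fraction.* That needs regimen omitted, nothing else carrying its effect, and the model fitted to imputed data. The SAP points to the Missing data section but does not state the last.
- *The primary treatment effect is biased.* Nothing here shows that.
- *Centre must also be in the imputation model.* Sensitivity analysis 1 targets the treatment effect, not centre coefficients. No harm has been quantified, and up to six more terms per arm sit badly with the SAP's small-sample rationale.
- *The imputation model is chosen after unblinded outcomes are seen.* The SAP says that participants and investigators cannot be blinded, and is silent on what the analyst sees.

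**Conclusion.** The point holds in a limited form. The stated selection rule does not secure regimen a place in each arm's imputation model, although the pre-specified subgroup model contains regimen and its interaction with treatment.

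If regimen is omitted and the interaction is estimated from imputed data, it is attenuated. The upper bound is about the missing fraction, reached when only baseline time in range is in the model; participants who leave before mid-study are in the same position. At 10% to 20% missing the loss is roughly 3% (mid-study time in range included and observed, 10% missing) to 22% (baseline only, 20% missing). These figures rest on assumed interactions of 5 to 6 points and a mid-study correlation of 0.7. The harm is attenuation and lost power in a secondary analysis, without inflated false positives. It merits a wording change because the better rule is nearly free.

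**What to change.** Replace the sentence on variable choice in the Missing data section with a fixed core. For example:

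> In each arm the imputation model for the primary outcome always contains baseline time in range (continuous) and insulin regimen, with mid-study time in range as an auxiliary variable. Correlation with the outcome is used only to add further auxiliary variables, never to remove a variable of an analysis model.

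In the subgroup section, also state whether the interaction model is fitted to the imputed data. The statistical price is about one extra parameter per arm for regimen, with about 60 participants per arm. No new data are needed and the primary analysis model is unchanged.

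### Filling missing outcomes with the arm median before a Wilcoxon test gives a type I error of about 10% at 10% missing and about 22% at 20% missing, against a nominal 5%

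*SAP*

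**What the plan says.** The primary analysis is an ANCOVA on the entire study population, with missing outcomes multiply imputed separately by arm (20 or 40 imputations). If the residuals are unsatisfactory, the outcome is log-transformed. If that fails too, Section 6, Primary outcome, Analysis methods says: "If the ANCOVA model still displays poor fit, non-parametric analysis (Wilcoxon rank sum test) will be employed". The glucose and clinical secondary outcomes have the same rank sum fallback, and the psychosocial, sleep and cognitive outcomes have an unnamed non-parametric one.

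For missing data in this branch, Section 6, Missing data says: "simple imputation will be performed, replacing the missing value with the median of the treatment arm". No adjustment of the variance for the filled values is described.

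Section 4 sets the error rate: "All hypothesis testing will be two-sided with an α of 0.05", with 95% confidence intervals. Section 3, Sample size gives the scale of missingness to expect: "Allowing a drop-out rate of 10% a total of 120 people will be recruited, 60 randomized to HCL while 60 randomized to control group". It also gives a more conservative scenario with 20% drop-out. For the primary outcome, fewer than 10 representative CGM days also counts as missing, so missingness can exceed drop-out.

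**The concern.** A filled value adds no information. It repeats the observed median of its own arm, so when that median is high by chance, every filled value in the arm is high with it. The rank sum test treats the filled values as separate, independent participants. Two things follow. The statistic varies more than the test allows for, because the arm's sampling error is counted again. In addition, the two blocks of filled values are compared with each other as blocks, so the arm with the higher median wins all of those pairs, however small the difference.

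Both effects arise with no treatment effect and with missingness unrelated to anything. If the branch is used, the test cannot hold the two-sided 0.05 of Section 4, and the interval for the median difference is too narrow. For the primary outcome, a false claim for or against HCL becomes more likely. For the secondary outcomes, individual p values would be reported at a nominal level they do not have.

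**Working it through.** **Inputs from the SAP.** Two-sided alpha 0.05 (Section 4); 60 randomised per arm; 10% and 20% drop-out (Section 3, Sample size); Wilcoxon rank sum test with arm-median fill (Section 6). **Assumptions added here:** no treatment effect, and outcomes missing completely at random.

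**The plan's own figure.** The design target is a 5-point difference, SD 9 points, 80% power and two-sided 5% error, for which the SAP states 104 evaluable participants. The normal approximation gives 2 × (1.960 + 0.842)² × 9² / 5² = 50.9, so 51 per arm. The t-test solution is 51.84, so 52 per arm and 104 in total, as stated. 104 / 0.90 = 115.6, so 120 covers 10% drop-out. The SAP's sample size is reproduced, and 60 per arm is the right size for the check.

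**Approximation by hand.** Let n = 60, let m be the fraction missing in each arm and n₀ = n(1 − m). Let θ be the Wilcoxon statistic U divided by n², which is expected to be ½ under the null. After the median fill,

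θ − ½ ≈ (1 − m)² W + 2m(1 − m) D + (m²/2) × sign(D)

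W is the same quantity from observed pairs only, with variance 1/(6n₀). D is the difference in observed medians times the density at the median, with variance 1/(2n₀). Their covariance is 1/(4n₀). The last term is the block-against-block comparison. The test assumes a standard error of √[(2n + 1)/(12n²)] = √(121/43,200) = 0.0529. The tie correction barely changes this.

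*10% missing* (n₀ = 54, six filled per arm):
- variance of the first two terms = (0.81²/6 + 2 × 0.81 × 0.18/4 + 0.18²/2)/54 = (0.1094 + 0.0729 + 0.0162)/54 = 0.00368, SD 0.0606
- the test rejects when |θ − ½| exceeds 1.96 × 0.0529 = 0.1037; the block term supplies 0.1²/2 = 0.005 of that
- (0.1037 − 0.005)/0.0606 = 1.63, two-sided probability 10.3%

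*20% missing* (n₀ = 48, twelve filled per arm):
- variance = (0.64²/6 + 2 × 0.64 × 0.32/4 + 0.32²/2)/48 = (0.0683 + 0.1024 + 0.0512)/48 = 0.00462, SD 0.0680
- threshold 0.1036 after the tie correction; block term 0.2²/2 = 0.02
- (0.1036 − 0.02)/0.0680 = 1.23, two-sided probability 21.9%

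**Simulation.** 40,000 null trials per setting, 60 per arm, tie-corrected rank sum test, eight outcome shapes (normal, lognormal, exponential, beta, left-skewed, t with 3 df, uniform, bimodal):

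| Missing per arm | Arm-median fill | Approximation above |
|---|---|---|
| 0% | 4.9–5.2% | – |
| 5% | 6.9–7.3% | 7.1% |
| 10% | 10.2–10.4% | 10.3% |
| 15% | 14.6–15.2% | 15.1% |
| 20% | 21.2–21.9% | 21.9% |
| 30% | 43–44% | 43.1% |

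The same test on observed values only gives 4.7% to 5.2% throughout.

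**Variations.**
- Continuity-corrected test with a random number missing per arm (8,000 trials): 10.9% at 10% and 22.4% at 20%.
- Unequal missingness: 9.9% with 5% and 15% missing in the two arms; 20.6% with 10% and 30%.
- 30 per arm, roughly the size when each regimen is analysed separately and recruitment is balanced: 9.5–9.8% at 10% and 17.9–18.3% at 20%.

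**Intervals.** With a normal outcome, an assumed SD of 12 points and 3,000 trials per setting, the rank-based 95% interval for the median difference covers the true value about 90% of the time at 10% missing and about 79% at 20%. At 20% its mean width is 6.5 points, against 10.0 points from observed values only.

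**The case against.** The strongest defence is that this is a second-stage fallback. The primary analysis is ANCOVA on multiply imputed data, and median fill applies only if the residuals fail and the log transformation does not help. Nothing in the SAP says that this is likely for time in range. This stands: the 10% and 22% are error rates given that the branch is used, not the trial's overall type I error.

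For the primary outcome there is also a complete-case sensitivity analysis. In this branch it would most naturally be a Wilcoxon test on observed values, so readers would see a sound comparison (under missing completely at random) beside the inflated one. This also stands, but it leaves the headline p value wrong. The glucose, clinical and psychosocial outcomes are stated to have no sensitivity analysis, so nothing there would expose the problem.

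Secondary outcomes are declared exploratory, and their sections do not mention imputation, so one could argue that the fill is not meant for them. However, the Missing data section speaks of outcome variables in general. The exploratory label explains the absence of a multiplicity correction; it does not justify single tests that reject at two to four times their nominal level. The branch is also more plausible there: time below 2.8 mmol/L or above 16.7 mmol/L and lapse counts are likely to be skewed, and any zeros cannot be log-transformed.

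Finally, repeat CGM collection may keep missingness below 10%. At 5% missing the error is about 7%, which is modest. The 20% figure is the SAP's own conservative scenario. The 30% figure lies beyond both drop-out scenarios, although the Missing data section does provide for more than 30% missing.

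**Conclusion.** The concern holds. Arm-median single imputation followed by a Wilcoxon test is incompatible with the stated two-sided 0.05. If the fallback is used at 60 per arm, the type I error is about 10% at 10% missing (about twice nominal) and 21% to 22% at 20% missing (a little over four times nominal). In regimen subgroups of about 30 per arm, the 20% figure is about 18%, or 3.6 times nominal. The results assume no treatment effect and outcomes missing completely at random. They barely depend on the shape of the outcome, and a large-sample approximation agrees with the simulation. Because the rule is pre-specified for the primary test and is invalid whenever an appreciable share of outcomes is missing, it must be corrected, even though it may never be reached for time in range.

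**What to change.** Delete the median-imputation sentence from Section 6, Missing data, and name one replacement.

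For the primary outcome, the option closest to the SAP's whole-population aim is to keep multiple imputation by arm, compute a rank-based or robust estimate with its standard error in each imputed data set (preferably adjusted for baseline), and pool the estimates with Rubin's rules. The existing multivariate normal imputations should not be reused without thought, because this branch is entered when regression assumptions have failed. The SAP should name a model suited to the outcome, such as predictive mean matching.

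For the exploratory outcomes, a Wilcoxon test on observed cases is a simple alternative, with its missing-completely-at-random assumption stated. It could also serve for the primary outcome, but the SAP would then have to say that this branch departs from the entire study population. In no case should a single arm-specific value be imputed.

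The cost is a few lines of SAP wording and some programming; no new data are needed and trial conduct does not change. Intervals in this branch will be wider and p values usually less favourable, although under missing at random the estimate itself could move either way.
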